## Research Design and Methods

Describe in detail the methods and procedures that will be used to accomplish the objectives and specific aims of the project. Discuss the alternative methods that are available and justify the use of the method proposed in the study. Justify the scientific validity of the methodological approach (biomedical, social, or environmental) as an investigation tool to achieve the specific aims. Discuss the limitations and difficulties of the proposed procedures and sufficiently justify the use of them. Discuss the ethical issues related to biomedical and social research for employing special procedures, such as invasive procedures in sick children, use of isotopes or any other hazardous materials, or social questionnaires relating to individual privacy. Point out safety procedures to be observed for protection of individuals during any situations or materials that may be injurious to human health. The methodology section should be sufficiently descriptive to allow the reviewers to make valid and unambiguous assessment of the project. (DO NOT EXCEED TEN PAGES, USE CONTINUATION SHEETS).

Reference is made to the "Time schedule" at the end of this section "Research Design and Methods".

### Study population and subjects

Preschool children, age 3-7 y of both sexes will be selected from the urban slum in Mirpur, a suburb of Dhaka which is 10 km from the International Centre for Diarrhoeal Disease Research, Bangladesh (ICDDR,B): Centre for Health and Population Research. Mirpur slum is subdivided into camps covers a large area with a very high population density and poor housing. It is estimated that more than 3,000 children between 3 and 7 y live in the study area. Both the subjects and the study area are suitable for this study. Preschool children are known to suffer from the major health effects of vitamin A deficiency. Data from 2 merged studies have shown that children 3-6 y in Mirpur slum have a high prevalence of vitamin A deficiency, 53% (n=286) had serum retinol concentrations below  $< 0.70 \mu\text{mol/L}$ , even though there is a national vitamin A programme of biannual capsule supplementation. The prevalence of vitamin A deficiency (serum retinol concentrations below  $< 0.70 \mu\text{mol/L}$ ) subdivided into age groups was: 3-4 y, 49% (n=145); 4-5 y, 58% (n=128); and 5-6 y, 56% (n=13), respectively ([name] *et al.*, 1998; [name] *et al.*, 2001).

Mola is not eaten frequently in the study area and assembling this age group in one place in order to serve one meal per day is considered most appropriate. The study site and population are already familiar to ICDDR,B, being used for different health research studies which have been conducted or are presently being carried out. ICDDR,B has a local office in the Mirpur slum, which employs both ICDDR, B professionals and local community people. There are good infrastructure, records of the area and households as well as a good rapport and collaboration with the community leaders and inhabitants. The short distance from the study area to the ICDDR,B facilities (with electricity, laboratory, storage and freezer) is crucial for carrying out the study successfully.

The selected children will be randomly across age range and gender and the children enrolled in the study will be randomly allocated to three intervention groups. Differences in age and gender are not expected to effect the output of the study. However, the effect of these variables will be taken into consideration in the statistical analysis.

In Bangladesh, there are three distinct seasons with respect to food availability - winter, summer and monsoon. The study will be conducted in winter for a period of 9 weeks, in which the habitual food pattern will be similar.

### Design and intervention groups

A house to house survey will be conducted in about 4 camps purposely selected in order to achieve proposed target children (inclusions criteria in points 1-4 on the next page and **Appendix 1: Household mapping form**).

For the intervention study only marginal vitamin A deficient children (based on serum retinol concentrations 0.35-0.70  $\mu\text{mol/L}$ ) will be selected, since only in these children is the intervention expected to have an increase in serum retinol concentration. Expecting that one out of three children (33%) has marginal vitamin A deficiency, approximately 550 children who meet the inclusion criteria listed in points 1-7 below, will be *screened* to determine their serum retinol concentration.

Children who meet all of the following inclusion criteria will be selected for *screening*:

1. Preschool children of both sexes between 3 and 7 years of age from families of lower socio-economic status
2. Children who eat fish
3. Taking no vitamin A supplementation and multivitamin in the preceding 6 months
4. Not suffering from serious illness like: persistent or chronic diarrhoea, tuberculosis, chronic pneumonia disease, asthma, diabetes type 1, hepatitis B, cardiac malformation, measles, respiratory tract infections, acute diarrhoea and skin infections
5. Parents and children who give their consent to participate in the study
6. Children who pass the clinical health examination (Appendix 2: Child clinical health examination form): For example having no clinical signs of vitamin A deficiency, chronic diseases, measles, respiratory tract infections, acute diarrhoea, skin infections and severe malnutrition
7. On the time of blood drawing, have no fever and show no clinical sign of acute infections, including diarrhoea

Children (n=180) identified as marginal vitamin A deficient (based on serum retinol concentrations 0.35-0.70  $\mu\text{mol/L}$ ), will be randomly allocated to either of the following three intervention groups and enrolled in the feeding trial at *baseline*. In each intervention group, there will be 60 children, receiving the same basic meal and either:

- 1) small fish, mola (vitamin A rich group) or
- 2) big fish, rui (negative control group, no/low vitamin A) or
- 3) rui and purified vitamin A, retinyl palmitate (positive control group)

All children will receive one meal per day, replacing one of the meals at home for 6 days a week for 9 weeks.

The negative control group is included because changes in serum retinol over time may be related to factors other than the small fish, such as seasonal variation and infection. The positive control group, receiving pure retinol is included in order to determine the maximal change in serum retinol.

## Methods

### *Before screening for vitamin A deficiency*

Children (n=550) will be clinically health examined (Appendix 2: Child clinical health examination form), stool will be collected (for later assessment of the degree of parasitic infestation) and the children will be given anti-helminthic treatment (albendazole tablets, 400 mg). All children will be given anti-helminthic treatment, as it is common in the study area that children have worms. It has been found that >90% children are infected in Mirpur slum (Hall *et al*, 1992). Two weeks after the first deworming a second deworming (albendazole tablets, 400 mg) will be given in order to ensure that all the children is free of worms. Deworming will be beneficial for the children's health. In addition, deworming of the children prior to the feeding trial may maximise the efficacy of the intervention, since helminths have shown to reduce vitamin A absorption.

### *At screening*

Ten days after the second deworming, children will be clinically health examined, anthropometry will be measured and one blood sample will be drawn (Appendix 2: Child clinical health examination form). The feeding trial will begin (at *baseline*) after the *screening*. The *screening* including the analysis of serum retinol concentration will last for about 6 weeks.

Severely vitamin A deficient children (serum retinol concentration <0.35  $\mu\text{mol/L}$ ) will not be enrolled in the feeding trial, but referred to a medical doctor for necessary treatment including vitamin A supplementation.

The values of the biochemical indicators from blood collected at *screening* will be used as the *baseline values* for children enrolled in the feeding trial. This will be done in order to reduce the discomfort of the child in connection with blood drawing and the cost of analyses. The biochemical indicators in the blood are expected to be unchanged from *screening* to *baseline* or any changes are expected equally distributed across intervention groups.

### *Collection of baseline information of the households and the screened children (n=550):*

In addition to the above, the following baseline information will be collected from the households and *screened* children in a period of about 5 weeks, starting 6 weeks before *baseline*:

a) socio-economic data of the households (Appendix 3: Household socio-economic form), b) the risk of dietary vitamin A deficiency (based on one interview per child, - Appendix 4: Semi-quantitative dietary assessment of vitamin A), c) food and nutrient intake (based on one 24 h recall interview per child, - Appendix 5: Dietary intake assessment by 24 h recall) and d) morbidity data (based on one registration of incidence within the last 30 days, - Appendix 6: Morbidity form).

#### ***At baseline***

Marginal vitamin A deficient children (n=180), who have been randomly allocated to either of the three intervention groups will be clinically health examined and anthropometry will be measured (Appendix 2: Child clinical health examination form). In addition, on a subsample of children (15) in each of the 3 intervention groups the RDR test will be conducted. The RDR test is thought to be a reliable test for individuals liver reserve.

#### ***Between baseline and endpoint (feeding trial)***

During the feeding trial, all children will receive one meal per day, replacing one of the meals at home for 6 days a week for 9 weeks. The children will eat the other meals and snacks at home as usual. Twenty-four (24 h) dietary recall interview (Appendix 5: Dietary intake assessment by 24 h recall) and morbidity data (Appendix 6: Morbidity form) of all children will be collected biweekly. In addition, duplicate portions of dishes will be collected for nutrient analyses.

#### ***Endpoint***

At *endpoint*, children will be clinically health examined and anthropometry will be recorded (Appendix 2: Child clinical health examination form). One blood sample will be collected from all children. An additional blood sample will be collected for the RDR test. This will be done on a subsample of children (15) in each of the 3 intervention groups.

At the completion of the feeding trial, all children will be supplemented with vitamin A.

#### ***Mothers' perceptions of the effect of the mola supplementation***

At *endpoint* a qualitative questionnaire (Appendix 7: Perception of mola form) will be conducted (in the mola fish group) to evaluate the effect of the mola supplementation on the general well being of the children as well as the acceptance of the proposed mola meal for habitual use among the children and their families.

The mothers will be asked how the children felt after eating the test meal, how well they like the test meals and what benefits they think the test meal have on the nutritional status of their children. The mothers will also be asked if they will prepare the mola test meal at home and which resources they need to do so as well as which constraints they may face and how they can overcome these constraints.

This data from this questionnaire are important for large scale implementation of the results of this study, taking into account factors such as socio-economic status of the household and specific constraints for consuming mola.

Both structured and open ended questionnaire will be used to assess the perception of the mothers about mola fish. A focus group discussion with 15 mothers at 3-4 sessions will be conducted to assess the perception.

#### **Calculation of sample size**

Using retinol rich foods, fruit or vegetable, de Pee *et al* (1998a) found an increase in serum retinol of 0.23  $\mu\text{mol/L}$ , 0.12  $\mu\text{mol/L}$ , 0.07  $\mu\text{mol/L}$  respectively from a baseline of approximately 0.70  $\mu\text{mol/L}$  in a 9 weeks' intervention study in children 7-11 y. A dose of 650 RE/d given in two meals daily was used. The maximum standard deviation, 0.17  $\mu\text{mol/L}$  in the change in serum retinol from baseline to the end of the study was found in the fruit group.

The expected increase in serum retinol in the mola group in this study, 0.15  $\mu\text{mol/L}$  is based on an expected increase which is lower than that found in the group given the retinol rich food but higher than that in the group given fruit. Children in the positive control group might show a similar or a larger increase in serum retinol concentration than the mola group.

Assuming similar prevalence and distribution of serum retinol concentration at baseline in Bangladeshis as in the Indonesian children, about 0.70  $\mu\text{mol/L}$  and the expected increase amounts to a 20% increase from the baseline value.

The number of participants in each group,  $n$  is calculated from power calculations based on the following formula (Armitage & Berry, 1987):

$$n = [(Z_{\alpha} + Z_{\beta})^2 * (sd_1^2 + sd_2^2)] / d^2$$

$$Z_{\alpha} = 1.96 \text{ for } \alpha = 0.05, \quad Z_{\beta} = 1.28 \text{ for } \beta = 0.10 \text{ (power of 0.90)}$$

$sd_1, sd_2$  = standard deviation of the change in serum retinol from baseline to the end of the study for group 1 and group 2  $sd_1 = sd_2 = 0.20 \mu\text{mol/L}$

$d$  = difference in change in serum retinol between group 1 and group 2,  $d = 0.15 \mu\text{mol/L}$

The sample size required in each group is 37. Assuming a maximum possible drop out of 40%, the total number of children in each intervention group is calculated to be approximately 60. The total number of children to be used in this study is 180.

### Test meals

A pilot study was conducted in the Mirpur slum in October 2000 to develop and test the recipes to be used in the study as well as the procedures and the logistics, in terms of physical set up and manpower of carrying out the study. The dishes developed were cooked and served to 20 children for 5 days. Based on their feedback, adjustments were made. Samples of raw mola and rui and the corresponding cooked fish curries were taken to determine cooking loss of vitamin A. Samples of the cooked vegetable curries were also taken for determination of vitamin A.

The test meals in the different intervention groups have been designed in such a way that they appear and taste as similar as possible. The test meals will consist of rice, a fish curry and a vegetable curry. All foods given in the test meals other than mola are non/low vitamin A rich foods. Rice will be given *ad libitum* in order to adjust for the differences in energy needs due to different ages. Subsequently, all children are given the same fixed amount of rice, the few children who ask for more will be given more. The fish curry to be used in the intervention groups will differ only with respect to the fish species either small fish, mola or big fish, rui. The other ingredients of the fish curry will be onion, garlic, ginger, turmeric, chilli seed, iodised salt and soybean oil. The amount of cooked fish curry used in the intervention groups is fixed to correspond to either 45 g raw cleaned mola or rui/child/meal. The cooked mola curry will be homogenised (blended) so that the vitamin A in mola is uniformly distributed throughout the whole amount. The rui curry will also be homogenised. It was observed that the two fish curries differed in colour, the mola curry being dark green and the rui curry had a yellow tinge. The same vegetable curry will be used in all intervention groups during the study and will be served in a fixed amount. The vegetable curry will consist of bottle gourd in addition to potato, cucumber, onion, mug dal, garlic, ginger, turmeric, chilli seeds, iodised salt and soybean oil.

The recipe for 200 children are shown in appendix 14. However, we shall offer cooked rice 400g, vegetables 200g and blended fish (mola/rui) curry 90 g.

In the positive intervention group, retinyl palmitate solution will be added to the meal of each child at serving. In order to ensure that the vitamin A recommended intake is met in the vitamin A rich and positive control groups, the daily test meal will contain approximately 500 RE/d.

Mola (300 kg) and rui (1100 kg) will be caught over a period of 4-6 months (starting at the end of 2001 and completing in the beginning of 2002). The fish will be cleaned, packed, weighed in daily portions and stored frozen at the Mymensingh Aquaculture Extension Project until transport to Mirpur. The rice (2400 kg) will be purchased from the Bangladesh Rice Research Institute. The vegetables (6500 kg) will be supplied by a local wholesale vendor.

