### Hypothesis to be Tested

An intake of 45g vitamin A rich small fish (mola, *Amblypharyngodon mola*) improves vitamin A status in Bangladeshi preschool children with marginal vitamin A deficiency.

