Preformed vitamin A, which is found in foods of animal origin, is more efficiently absorbed than most carotenoids and more effective in improving vitamin A status (National Research Council, 1989). However, these foods are considered as not being easily available to and affordable for poor households. Within food based strategies, there has been no focus on the role that small fish can play in preventing and combating micronutrient deficiencies. Small fish is a commonly consumed food in many developing countries and are easily available, relatively cheap and well liked by most household members, including children. In Bangladesh, small fish rank third with respect to amount of raw food intake after rice and vegetables in many communities for large parts of the year ([name] *et al*, 1997). Some commonly consumed small fish species have been found to have extremely high contents of preformed vitamin A (Roos, 2001). For example, mola contains 2,400 - 3,000 RE/100 g raw edible fish (Roos, 2001), 5 times higher than the green leafy vegetable, amaranth (*Amaranthus gengeticuss*) (Varming, 1996). Few other indigenous small fish species in Bangladesh have been identified to have very high contents of vitamin A, chanda (*Parambassis baculis*) (> 1500 RE/100 g raw edible fish); dhela (*Osteobrama cotio cotio*) and darkina (*Esomus danricus*) (500-1,500 RE/100 g raw edible fish) while several other species have been found to have medium contents of vitamin A (100-500 RE/100 g raw edible fish) (Roos, 2001). However, the bioavailability of vitamin A from these small fish still needs to be established. An intake of 45 g mola/d (2,400 RE/100 g raw edible fish) meets the full daily vitamin A recommended dietary allowance of 4-6 years old children (500 RE/d) (National Research Council, 1989), taking a cooking loss of about 50 % into consideration. A pilot trial has shown that children can easily consume 45 g of fish (given as 60 g of fish curry) and even higher amounts, 70 g of fish (given as 90 g of fish curry) from a single main meal (own observations). No study has looked at the efficacy of a daily amount of vitamin A rich small fish on the vitamin A status in humans.

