#### **Preliminary Observations**

International Centre for Diarrhoeal Disease Research, Bangladesh (ICDDR,B): Centre for Health and Population Research (ICDDR,B) and the principal investigator have been conducting different scientific research in the proposed study area, Mirpur slum in Bangladesh for the past 7 years. Mirpur slum is a suburb of Dhaka, which is 10 km from ICDDR,B. The short distance from Mirpur slum to ICDDR,B facilities makes it feasible to carry out field studies in the area. In addition, ICDDR,B has a local office in the Mirpur slum, which employ both ICDDR, B professionals and local community people. There are good infrastructure, records of the area and households as well as a good rapport and collaboration with the community leaders and inhabitants in the area. Based on previous ICDDR,B studies, the population in this area suffer from various micronutrient deficiencies such as vitamin A, iron and zinc deficiency.

A pilot study was conducted at the local office in the Mirpur slum in October 2000 to develop and test the recipes to be used in the study as well as the procedures and the logistics, in terms of physical set up and manpower of carrying out the study.

The test meals in the 3 different intervention groups have been designed and will consist of rice, a blended fish curry and a vegetable curry. The dishes developed were cooked and served to 20 children (4-11 yrs age) for 5 days. Cooked rice (200-450g on various days), and cooked vegetables 200g were offered and eaten by the children. Cooked and blended *mola, rui fish* (60 g on day 1-3 and 90 g rest days) were eaten by the children. Based on their feedback, adjustments were made with respect to ingredients in each recipe and amount of each dish to be served in the test meal. Based on the children's behaviour and reactions, it was observed that they needed motivation to eat the test meals, at least initially, but at the same time, they liked the dishes, expressing that they were very tasty.

Samples of raw mola and rui and the corresponding cooked fish curries were taken to determine the cooking loss of vitamin A. Samples of the cooked vegetable curries were also taken for determination of vitamin A but these have not yet been analysed. We assumed that the cooking loss of vitamin A could be maximum 50%.

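### The Test meals section ties the fish curry to 45 g raw fish but then orders a 90 g serving, which holds about 1.3 to 1.6 times that amount of mola

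*Protocol*

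**What the plan says.** The hypothesis is stated for one portion: "An intake of 45g vitamin A rich small fish". The overall aim repeats 45 g and gives 500 RE for the mola and 500 RE for the retinyl palmitate added to rui.

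The Test meals section carries this into the kitchen: "The amount of cooked fish curry used in the intervention groups is fixed to correspond to either 45 g raw cleaned mola or rui/child/meal". Its paragraph on the meals then closes by pointing to the Appendix 14 recipes and adding: "However, we shall offer cooked rice 400g, vegetables 200g and blended fish (mola/rui) curry 90 g". The paragraph after it says of the vitamin A rich and positive control groups that "the daily test meal will contain approximately 500 RE/d".

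The Background reports what the pilot children could eat, and so supplies a conversion between raw fish and cooked curry: "45 g of fish (given as 60 g of fish curry" for the smaller portion and "70 g of fish (given as 90 g of fish curry" for the larger. The Preliminary Observations confirm that these were two separate servings on different days: "60 g on day 1-3 and 90 g rest days) were eaten by the children".

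On the role of the retinyl palmitate arm, Design and intervention groups says: "The positive control group, receiving pure retinol is included in order to determine the maximal change in serum retinol".

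**The concern.** On the pilot's own conversion, 90 g of curry is the larger pilot portion, not the 45 g one. Staff weigh each child's curry, so they need a single number. The only curry weight given as an instruction in the methods is the one that does not fit the 45 g portion.

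Two things depend on it. A positive result at a larger portion would not show that 45 g works, and 45 g is the amount the protocol links to the recommended daily allowance. The retinyl palmitate is also added to each child's meal separately at serving, so it does not grow with the curry. A larger mola portion therefore breaks the nominal dose match between the two vitamin A arms. In nominal RE, the arm included to show the largest attainable change would then receive less than the arm under test.

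**Working it through.** **Inputs.** Portion 45 g raw fish (hypothesis, overall aim, Test meals). Serving 90 g curry (Test meals). Pilot pairs 45 g fish to 60 g curry and 70 g fish to 90 g curry (Background). Mola content 2,400 RE per 100 g raw, with about 50% cooking loss (Background). Ingredient weights and head-counts (Appendix 14). Retinyl palmitate 500 RE (overall aim).

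**The plan's own dose.** 45 g × 24 RE/g × 0.5 = 540 RE, which agrees with the stated approximate 500 RE.

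**Raw fish in 90 g of curry**

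1. Pilot figure taken directly: 70 g, and 70/45 = 1.56.
2. Smaller pilot pair scaled up: 90 × 45/60 = 67.5 g, and 67.5/45 = 1.50.
3. Mola recipe: 3,000 + 1,000 + 20 + 80 + 50 + 27 + 70 + 370 = 4,617 g. Then 90 × 3,000/4,617 = 58.5 g, and 58.5/45 = 1.30.
4. Rui recipe, counting the fish at raw weight: 6,000 + 2,000 + 40 + 160 + 100 + 53 + 140 + 740 + 1,340 = 10,573 g. Then 90 × 6,000/10,573 = 51.1 g, and 51.1/45 = 1.13.

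Lines 3 and 4 use listed weights with no evaporation. Loss of water in cooking would raise both. Line 3 also assumes that the unweighed water in the freezing bag is only drip from the fish. For 90 g of mola curry to hold just 45 g, the batch would have to weigh 3,000 × 90/45 = 6,000 g. That is 6,000 − 4,617 = 1,383 g more than the recipe lists.

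**Which portion the recipes are built for.** Mola: 3,000 g for about 65 children is 46.2 g each. Rui: 6,000 g for about 130 children is also 46.2 g each. One mola batch cannot supply 60 children at 90 g: 60 × 90 = 5,400 g, against 4,617 g listed.

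**Nominal mola dose if 90 g is served**

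| Raw mola | RE (g × 24 × 0.5) | Ratio to 500 RE |
|---|---|---|
| 45 g (intended) | 540 | 1.08 |
| 58.5 g (recipe) | 702 | 1.40 |
| 70 g (pilot) | 840 | 1.68 |

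The portion alone accounts for 702/540 = 1.30 to 840/540 = 1.56. The remaining 1.08 is already there at the intended portion.

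**Curry weight that holds 45 g raw fish.** Mola: 60 g by the pilot, or 45 × 4,617/3,000 = 69 g by listed weights. The two agree if the batch cooks down to 60 × 3,000/45 = 4,000 g, a loss of 617/4,617 = 13%. Rui by listed weights: 45 × 10,573/6,000 = 79 g. On listed weights, no single curry weight gives 45 g of fish in both dishes.

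**The case against.** The strongest reply is that 90 g is one stray sentence. The hypothesis, the aims, the sentence fixing the portion, the 500 RE target and the head-counts in both recipes agree on 45 g. This stands as evidence of intent, and it is why the repair is to the serving weight. It does not make the sentence harmless, because that is the figure staff would weigh to. The daily and total kitchen quantities do not support 90 g either. They are large enough for both portions, whereas the recipe head-counts point to 45 g.

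A reader might go further and infer that the plan gives the two vitamin A arms different doses. The documents do not say so. Test meals still states about 500 RE for both meals, and the mismatch arises only if 90 g is served. A reader might also infer that mola would exceed the retinyl palmitate arm in active vitamin A. That cannot be concluded, because most of the vitamin A in mola is dehydroretinol and the protocol does not say whether its RE values already allow for the lower activity of that form. The comparison here is in nominal RE only.

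Three further replies have some force:

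- The pilot pairs predate changes to the recipes, so 1.56 may not describe the trial dish. The listed trial recipe still gives 1.30 before evaporation.
- The 50% cooking loss is an assumed maximum. A smaller loss would raise the RE at every portion alike and leave the factor of 1.30 to 1.56 unchanged.
- Leftovers are weighed and the fish dishes are assayed weekly, so the achieved dose can be known. That comes too late to restore a dose match at serving.

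**Conclusion.** The two portions in Test meals contradict each other under every conversion in the protocol, and this much is firm. The rest of the document shows that 45 g is intended.

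The consequence is conditional. If 90 g is served as written, the mola portion is about 1.3 to 1.6 times the hypothesised one. The lower end rests on listed ingredient weights without evaporation, the upper end on the pilot conversion. That range is for mola only; the corresponding rui figure is about 1.13. The nominal mola dose would be about 700 to 840 RE against 500 RE, assuming 2,400 RE per 100 g and 50% loss.

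The damage is limited to two places: what can be claimed for 45 g, and the comparison of mola with retinyl palmitate. Mola versus plain rui remains a valid randomised comparison of the dishes as served. No input to the sample size formula depends on the portion. The figure should be corrected because it is an operating instruction, but it does not threaten the trial's validity.

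**What to change.** In Test meals, replace the 90 g curry figure with a rule for each dish: serve 45 g × (weighed cooked batch ÷ raw fish in the batch), calculated each day. Expect roughly 60 to 69 g for mola and possibly a different weight for rui. Do not write in 60 g as a constant: by listed weights before evaporation, 60 g of mola curry holds only 60 × 3,000/4,617 = 39 g of mola.

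The cost is one sentence and one division per dish per day. The Appendix 14 recipes already call for the whole curry to be weighed before portioning.

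If 90 g is truly intended, more has to change. Restate the raw-fish portion in the hypothesis, aims, summaries, the sentence fixing the portion and the recipes, and set the retinyl palmitate dose to the assayed vitamin A of that mola portion.
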